# 6.1.3 Pregnancy test

Female patients of child-bearing age, defined as those who menstruate and are aged over 18 years and married female patients aged above 12 years, will be asked to take a urine pregnancy test before enrolment in the study, because aretesunate-pyronaridine is contraindicated during pregnancy. They will also be asked to take a urine pregnancy test on day 42 or on early withdrawal from the study. Female participants of child-bearing age, defined as those who menstruate and are aged over 18 years, and who are sexually active should use barrier contraceptive devices for the duration of the study. Birth spacing pills will be provided by the investigator or study team at the time informed consent is obtained, with appropriate counselling about the risks of becoming pregnant and exposing the foetus to the study medicines.

# 7. Drugs and dosages

**Pyronaridine-artesunate** (Pyramax®, Shin Poong Pharmaceuticals). One tablet contains 60mg artesunate+ 180mg pyronaridine. Dosing will be according to body weight:

Body Weight(kg)	Daily dose(n	ng)	Number of tablets
	PYR	AS	
20-<24 kg	180	60	1 tab
24-<45 kg	360	120	2 tabs
45-<65 kg	540	180	3 tabs
65 ang above	720	240	4 tabs

Pyronaridine-artesunate will be taken orally with water, once daily for 3 days. Each dose will be administered under supervision in the clinic or if not possible by a home visitor to the patient's home. A dose will be repeated in full if vomiting occurs within 30 minutes of administration and halved if vomiting occurs between 30 minutes and 1 hour post dosing. This event will be documented in the case record form (CRF). Dosage tables are appended (Appendix 1).

#### 8. Rescue treatment and treatment

If the patient vomits twice the treatment he/she will receive parenteral therapy based on the national treatment guidelines. If a patient is unable to tolerate the trial medication he/she should discontinue the treatment and alternative anti-malaria medication should be initiated. In this case, the reason for discontinuation should be recorded in the case record form (CRF) as "Adverse experience" and be withdrawn from the study. The patient will receive parenteral therapy with artemether or quinine 7 days (IV) + tetracycline 7 days as well as relevant supportive treatments.

Any patient with signs of severe malaria, will be hospitalized and receive parenteral therapy with artemether or quinine 7 days (IV) + tetracycline 7 days as well as relevant supportive treatments. Recurrent infections with *P. falciparum* will be treated with a 3-day course of artesunate+mefloquine (A+M) according to the national treatment guideline and the patients will be followed up for 42 days.

An episode of *P. vivax* malaria during follow up will be treated with dihydroartemisinin-piperaquine (DHA-PIP) according to the national treatment guidelines and the patients will be followed up over 28 days.

# 9. Follow up (see table 1 in appendix)

- All patients will have a blood smear examined daily during the first week by microscopy until parasite clearance (2 consecutive negative slides on two consecutive days; both asexual and sexual stages). A negative blood slide will be defined as parasite count negative per 1000 WBC in two consecutive days. The sample on day 3 will be taken as close as possible to 72h after the initial blood smear.
- Blood biochemistry and basic haematology on D0, D3, D7 D14, D28 and D42. Tests for: AST/ALT, total bilirubin and alkaline phosphatase. If values increase, a confirmation test will be done within 48 hours where practical and clinically indicated. Regarding liver function tests (LFT), any elevation of ALTx3ULN on day 3 not having returned to baseline by day 7 will be followed up and repeated on day 28 and 42. A specific monitoring of LFT will be performed for any patient in which ALT values are greater than 3xULN combined with a bilirubin greater than 2xULN (Hy's law), or if ALT has risen to above x5ULN, irrespective of other accompanying abnormalities (cf Appendix 2 on "Adverse Event of Special Interest: drugs and the liver"). In such cases, LFT will need to be repeated twice a week until values return to baseline. Hy's law cases will need to be reported as a SAE (See Section 14.2). Total blood volume per time point for biochemistry and haematological assessments will be 2 mL.

*Time windows for follow-up visits:* 

The time-window for the visit on Day 7 is + 1 days, for the visits on Days 14 - 35 is -1 to +1 days and for D42 is -1 to +1 days. If patients do not attend for follow-up a home-visitor from the study team will try to locate the patient and bring them to the clinic.

#### 10. Treatment failures

Definition of treatment failures will follow the standard WHO definitions:

# Early treatment failure

- danger signs or severe malaria on day 1, 2 or 3 in the presence of parasitaemia;
- parasitaemia on day 2 higher than on day 0, irrespective of axillary temperature;
- parasitaemia on day 3 with axillary temperature ≥ 37.5 °C;

• parasitaemia on day  $3 \ge 25\%$  of count on day 0.

#### (Late treatment failure)

# Late clinical failure

- danger signs or severe malaria in the presence of parasitaemia on any day between day
   4 and day 28 (day 42) in patients who did not previously meet any of the criteria of
   early treatment failure;
- presence of parasitaemia on any day between day 4 and day 42 with axillary temperature ≥ 37.5 °C or history of fever in patients who did not previously meet any of the criteria of early treatment failure

#### Late parasitological failure

 presence of parasitaemia on any day between day 7 and day 42 with axillary temperature < 37.5 °C in patients who did not previously meet any of the criteria of early treatment failure or late clinical failure

#### Adequate clinical and parasitological response

• absence of parasitaemia on day 42, irrespective of axillary temperature, in patients who did not previously meet any of the criteria of early treatment failure, late clinical failure or late parasitological failure

# 11. Discontinuation/ Withdrawal of Participants from the Study

Each participant has the right to withdraw from the study at any time. In addition, the investigator may withdraw a participant if he or she considers it necessary for any reason including:

- Development of severe malaria.
- Repeated vomiting after administration of study drugs before the last dose study dugs.
- An adverse event or Disease progression which requires discontinuation of the study medication or results in inability to continue to comply with study procedures
- Significant non-compliance with treatment regimen or study requirements.
- Allergic Reaction to Study drugs after administration before the last dose study dugs.
- Liver function tests (AST/ALT levels) more than 2.5 times the upper limit of normal range.

If an individual is prematurely discontinued from study treatment for any reason, the investigator must make every effort to perform the following evaluations: physical examination and vital signs assessment, haematocrit level, parasite count and AE assessment. The reason for withdrawal will be recorded in the CRF. If the subject is withdrawn due to an adverse event, the investigator will arrange for follow-up visits until the adverse event has resolved or stabilised.

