# Main secondary endpoints:

• Absolute values and change from baseline related to hepatic biological values (ALT, AST, Total and conjugated bilirubin, alkaline phosphatase and any other relevant parameters if available) at day 0, 3, day 7 and day 28 and where available, any additional follow up values to confirm return to baseline values.

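### Section 11 allows withdrawal for AST/ALT above 2.5×ULN with no time limit, which risks losing hepatic and Day 42 data selectively in patients with raised liver tests

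*Protocol*

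**What the plan says.** Section 11 of the protocol, on discontinuation and withdrawal from the study, is permissive: "the investigator may withdraw a participant if he or she considers it necessary for any reason including" a list of six reasons. The last is "Liver function tests (AST/ALT levels) more than 2.5 times the upper limit of normal range". It repeats, word for word, an entry exclusion in Section 5.2 and carries no time point. Two other bullets are limited to the dosing period, for example "Allergic Reaction to Study drugs after administration before the last dose study dugs". For a subject withdrawn because of an adverse event, "the investigator will arrange for follow-up visits until the adverse event has resolved or stabilised".

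Section 9 sets the liver monitoring: "Blood biochemistry and basic haematology on D0, D3, D7 D14, D28 and D42". Extended follow-up starts higher than 2.5×ULN. First, "any elevation of ALTx3ULN on day 3 not having returned to baseline by day 7 will be followed up", with repeats on D28 and D42. Second, twice-weekly testing applies when ALT exceeds 3×ULN together with bilirubin above 2×ULN, "or if ALT has risen to above x5ULN, irrespective of other accompanying abnormalities".

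The main secondary endpoint in Section 3 is hepatic values and their change from baseline at D0, D3, D7 and D28, plus, where available, "any additional follow up values to confirm return to baseline values". Appendix 5 censors withdrawn patients in the Kaplan-Meier analysis at the last scheduled day before withdrawal and drops them from the per-protocol proportion.

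**The concern.** A withdrawal reason based on a laboratory value that is itself an endpoint makes missing data depend on the outcome. Patients whose transaminases rise may leave the schedule, while those with normal values stay. Later hepatic summaries, especially at D7 and D28, would then look more favourable than the truth, and the return to baseline would go unrecorded on the scheduled days in the patients for whom it matters.

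Liver safety is central to this trial. Section 17.1 reports enzyme elevations after this drug, and Section 12.3 names hepatotoxicity as an event of special interest. The same withdrawals also remove D28 and D42 outcomes from the primary efficacy endpoint.

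The rule also sits awkwardly with Section 9. Any patient who reaches a Section 9 trigger has already passed 2.5×ULN, so one section permits ending participation for patients whom another section requires to be followed.

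**Working it through.** **Order of thresholds.** 2.5×ULN, AST or ALT (withdrawal permitted, Section 11) < 3×ULN, ALT (repeat tests if unresolved by D7, or twice-weekly tests if bilirubin also exceeds 2×ULN, Section 9) < 5×ULN, ALT (twice-weekly tests whatever else is found, Section 9). Isolated AST rises, and ALT between 2.5× and 3×ULN, meet the withdrawal criterion but no extended Section 9 schedule.

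**Can the rule spare exposure?** Section 7 and Table 1 give one dose daily on D0, D1 and D2. The first scheduled post-dose biochemistry is on D3. No dose is left to stop when a scheduled post-dose result arrives.

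**What one withdrawal forgoes.** This assumes that scheduled visits stop.

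| Scheduled item | Source | Withdrawn on D3 result | Withdrawn on D7 result |
|---|---|---|---|
| Post-dose biochemistry: D3, D7, D14, D28, D42 | Section 9 | 4 of 5 | 3 of 5 |
| Post-baseline hepatic endpoint days: D3, D7, D28 | Section 3 | 2 of 3 | 1 of 3 |
| Slides: D7, D14, D21, D28, D35, D42 | Section 6.1.1 | 6 of 6 | 5 of 6 |

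**Precision of the primary estimate.** Section 5 assumes 90% efficacy and ±5 points. At 95% two-sided confidence (assumed, since Section 5 does not state it), n = 1.96² × 0.9 × 0.1 / 0.05² = 138.3, which reproduces the stated 138. Then 138 × 1.05 = 144.9, which reproduces 145. The half-width is 1.96 × √(0.09/n):

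- n = 138: 5.0 points
- n = 133 (5 fewer, illustrative): 5.1 points
- n = 128 (10 fewer, illustrative): 5.2 points

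**Possible shift in the efficacy proportion.** Take 138 patients with 13.8 expected failures, and exclude k patients whose failure risk is f. Apparent efficacy is 1 − (13.8 − k·f)/(138 − k). Both k and f are assumptions.

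| f | k = 7 | k = 14 |
|---|---|---|
| 0% | 89.5% | 88.9% |
| 10% | 90.0% | 90.0% |
| 30% | 91.1% | 92.3% |
| 50% | 92.1% | 94.5% |

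At f = 10%, the overall failure risk, there is no shift. Bias in efficacy therefore needs a link between liver elevation and treatment failure, and the protocol gives no information on one.

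**The case against.** The strongest defence is that the bullet was meant for baseline. It copies the entry exclusion, blood for biochemistry is drawn at inclusion, and a D0 result returned after the first dose would be a sensible reason to stop the remaining doses in an ineligible patient. That reading is plausible, but the text does not state it, and the bullet sits in a list headed as withdrawal from the study.

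The rule is also discretionary. Section 11 allows withdrawal for any reason, so deleting one example would by itself change little. This is correct, and it is why the remedy must also say what happens to follow-up. The contrast with the time-limited bullets is modest too, because the severe-malaria and non-compliance bullets have no time limit either.

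Other provisions recover some liver data. Section 9 asks for a confirmation test within 48 hours of a rise where practical and clinically indicated. Appendix 1 covers AST as well as ALT and expects clinically significant elevations to be followed until they stabilise or normalise. Section 12.1 counts a biological anomaly as an adverse event, so follow-up to resolution can apply. The hepatic endpoint accepts extra values, and the value that crosses 2.5×ULN is already on record. All of this stands and reduces the loss. None of it guarantees a D7 or D28 liver test or a D42 slide after withdrawal, and the evaluations that Section 11 lists at discontinuation include no liver test.

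Finally, Section 13 keeps every enrolled patient in the intention-to-treat population and summarises safety in it. Membership of an analysis set does not supply values that were never measured.

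**Conclusion.** The concern holds. As written, Section 11 permits withdrawal at any time for a liver result below the levels at which Section 9 intensifies follow-up. On a scheduled post-dose result, that withdrawal has no protective effect on dosing. The per-patient loss follows from the protocol's own schedule, provided that scheduled visits stop on withdrawal.

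The total effect is unknown. The protocol gives no rate of crossing 2.5×ULN, and nothing shows how often investigators would use this reason. Loss of precision is minor, and bias in efficacy is possible but unsupported by any figure in the document. The case rests on avoidable loss selected on the main secondary endpoint. It should be fixed because the correction costs almost nothing, although the expected effect is modest and uncertain.

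**What to change.** In Section 11, delete the 2.5×ULN bullet, or limit it to a D0 result that becomes available after enrolment and let it stop only the remaining doses. In either case, add a statement that a raised post-dose liver test does not end study follow-up: parasitology continues to D42, all scheduled and triggered liver tests continue, and the patient remains in the intention-to-treat and safety populations as Section 13 already implies. The added statement is the essential part.

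The cost is a short amendment to one section. The visits, slides and liver tests are already scheduled.

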#### 12. Safety reporting

Patients will be screened for common adverse events using and will be recorded in a predefined list of events, with in addition an open text field for non-listed events. Changes in liver enzymes will be recorded.

#### 12.1 Adverse Events (AEs)

An Adverse Event (AE) is a sign, symptom, syndrome, disease or biological anomaly suffered by a patient or a subject participating in a clinical study and receiving a medicinal product. This term does not imply a causal relationship with the concerned treatment. Clinical signs typical of an acute malaria episode will not be considered AEs unless the healthcare personnel considers these events as exceptional due to their evolution, their seriousness, or another factor related to these events.

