# 12.3 Adverse Events of Special Interest:

An adverse event of special interest (AESI) is an adverse event for which on-going monitoring is appropriate within the context of the study. These events necessitate complementary examinations in order to characterize and understand them.

AESIs in this study can be related to:

- Hepatotoxicity
- Neurotoxicity/seizures
- Cutaneous reactions/photo toxicity

The study team, as well as the relevant referral facilities, should be trained to take particular notice of symptoms/signs suggestive of the AESIs in this study:

- 1) clinical and biological signs of possible hepatotoxicity such as:
- fatigue, nausea, abdominal pain, dark urine, putty or mastic coloured stools, jaundice (vellowing of the whites of the eyes or skin) and itching
- ALT value >5xULN or ALT value >3xULN AND total bilirubin value >2xULN
- 2) clinical signs of possible cardio-toxicity
- Palpitations
- Seizures
- Pounding/pain in the chest area
- Fainting/Syncope.
- 3) clinical signs of possible neurotoxicity/seizures such as:
- Seizures
- Dizziness
- Pins and needles sensations
- Visions disturbance
- Difficulties coordination
- Tinnitus
- 4) clinical signs of possible cutaneous reactions/photo toxicity such as:
- Urticaria
- angioedema
- · Skin lesions
- · Itching pruritus
- Discoloration
- Dermatitis

In all the cases of hepatotoxicity, confirmed by the PI / investigators, the sponsor. Notification will occur through the use of an ad hoc AESI form.

The patients with the following elevations may require more intensive inquiry on the part of the investigator: ALT value that exceeds 5.0 times the upper limit of normal or ALT value

that exceeds 3.0 times the upper limit of normal AND a total bilirubin value that exceeds 2 times the upper limit of normal (Hy's law).

The investigator should then consult the treating Cambodian physician to obtain an hepatitis panel (Anti-HAV IgM, Anti-HBc IgM, HBsAg, and hepatitis C RNA), hepatitis E IgM antibody, cytomegalovirus (CMV) testing polymerase chain reaction (PCR) testing, pp65 antigen, or IgM antibody; Epstein Barr virus (EBV) viral capsid antigen IgM antibody; In addition, serum creatinine phosphokinase (CPK) and lactate dehydrogenase (LDH) would need to be measured. The treating Cambodian physician will ensure proper referral in case a diagnosis of non-malaria or study drug related pathology.

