#### 12.5 Reporting Procedures for Adverse Events

#### Adverse Events

The AEs, regardless of their seriousness and causal relationship to the study drug, arising between the signature of the informed consent form and the last study visit (as per the protocol), must all be recorded on the patient chart (AE recording section). When possible, the symptoms must be regrouped within a single syndrome or diagnosis. The healthcare personnel shall have to specify the date of manifestation of the event, its intensity, final evolution, the measures taken and the treatment undertaken (if any).

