Possible Hy's Law case following the FDA Guidance on Drug Induced Liver Injury: Premarketing Clinical Evaluation dated July 2009 A possible Hy's law case is defined as a subject with any value of ALT or AST above 3xULN together with an increase in bilirubin to a value higher than 2xULN and NOT associated to an ALP value higher than 2xULNA decision on medical and scientific grounds is required to assess whether an immediate notification of an event is warranted in other situations, such as medically important events which are not life-threatening, fatal or cause hospitalization, but could endanger the patient or could rendered necessary an intervention to prevent one of the above conditions to develop.

Remark: Examples of such events are intensive care in the emergency room or at home to treat a bronchospasm; a haematological dyscrasia; convulsions or an asymptomatic increase ALT ( $\geq 10 \text{ x ULN}$ ) not causing hospitalisation, or the development of drug addiction or abuse

TABLE 1: STUDY SCHEDULE

	D0	D1	D2	D3	D4	D7	D14	D21	D28	D35	D42	REPf		olumes
Screening													(ml) per time	
Written informed consent	X												adult	Child
Assign participant ID	X												≥16 yrs	<16yrs
Participant's history	X													
Symptoms checklist	X	X	X	X	X	X	X	X	X	X	X	X		
Vital signs	X	X	X	X	X	X	X	X	X	X	X	X		
Temperature	X	X	X	X	X	X	X	X	X	X	X	X		
General Examination	X	X	X	X	X	X	X	X	X	X	X	X		
Study Drug administration														
PYR-Artesunate	X	X	X											
Laboratory Procedures														
#Malaria blood film	X	X	X	X	X	X	X	X	X	X	X	X	0.5	0.5
HCT or Hb	X	X	X	X	X	X	X	X	X	X	X	X	0.03	0.03
Filter paper blots	X											X	0.3	0.3
FBC	X			X		X	X		X		X	X	1	1
Biochemistry	X			X	_	X	X		X		X	X	1	1
	X					X						X	0.5	0.5

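### Section 12.1 lets a new or worse section 12.3 warning sign soon after dosing be put down to malaria before it is recorded as an adverse event

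*Protocol*

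**What the plan says.** Section 12.1 first says that the term AE implies no causal link with treatment. It then deals with signs typical of an acute malaria episode: these "will not be considered AEs unless the healthcare personnel considers these events as exceptional due to their evolution, their seriousness, or another factor". It does not list the signs that count as typical, and it does not refer to the patient's state on D0.

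Four other places bear on what is recorded:

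- **Section 12** has patients screened for common adverse events, which "will be recorded in a predefined list of events, with in addition an open text field for non-listed events". The list itself is not shown.
- **Section 12.3** begins: "An adverse event of special interest (AESI) is an adverse event for which on-going monitoring is appropriate within the context of the study". Its pointers to hepatotoxicity start with "fatigue, nausea, abdominal pain", and its pointers to neurotoxicity include dizziness. The study team "should be trained to take particular notice of symptoms/signs suggestive of the AESIs in this study".
- **Section 12.5** covers "The AEs, regardless of their seriousness and causal relationship to the study drug", from consent to the last visit. For each event, staff must "specify the date of manifestation of the event, its intensity, final evolution, the measures taken and the treatment undertaken". Presumed cause is not among these items.
- **Table 1** schedules a "Symptoms checklist" at D0 and at every later visit.

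Section 3 places documented AEs and their relationship to study drugs among the other secondary endpoints. Section 4 describes a single-arm, open-label study.

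**The concern.** The default in section 12.1 is exclusion, and the way out is staff judgement that a sign is exceptional. A mild symptom that could come from the drug or from the resolving infection is therefore judged for cause before it is written down as an AE. That is the reverse of the usual order, and of the principle in sections 12.1 and 12.5 that AE status does not depend on cause.

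At stake is the completeness of the AE summary and of the drug-relationship assessment. With no control arm, nothing in the study shows how much early nausea or dizziness belongs to the disease. An analysis plan cannot recover an AE's intensity or relationship if the event was never recorded as one.

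**Working it through.** No formula applies and the plan states no figure to reproduce. The check follows one case through the text: mild nausea, absent on D0 and first reported on D2.

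1. **Section 12.1.** If staff regard nausea as typical of acute malaria, it is not an AE unless they find it exceptional. Evolution is a permitted ground, so they may record it. Ordinary mild nausea is not obviously exceptional, and no comparison with D0 obliges them to.
2. **Section 12.5.** The duty to record regardless of causal relationship applies to AEs. It does not reach a sign that section 12.1 has already set aside.
3. **Section 12.3.** A special-interest event is defined as a kind of AE, so it inherits the exemption. Training staff to notice nausea makes recording more likely, but the section does not say that it takes precedence over section 12.1. The same sign can be flagged in one section and exempt in the other.
4. **Section 12.** The text does not say that an event on the predefined list counts as an AE when it is also malaria-typical.
5. **Table 1.** The checklist should capture the symptom on D2 and its absence on D0, if nausea is one of its items. No rule turns a checklist entry into an AE.
6. **Appendix 3.** The D2 form has one yes/no question on the presence of an adverse event, with a name field and a seriousness question. Whoever answers it must apply section 12.1.

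**Period exposed.** Dosing is on D0 to D2, so drug effects and resolving malaria overlap mainly in the first days. A sign at D14 to D42 without recurrence does not naturally fit an acute malaria episode.

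**What covers part of the gap.**

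- Section 9 schedules biochemistry on D0, D3, D7, D14, D28 and D42 whatever the symptoms. Section 12.3 sets triggers at ALT above 5 times the upper limit of normal, or above 3 times with bilirubin above 2 times. Fatigue, nausea and abdominal pain as hepatic pointers therefore have laboratory tests behind them; dizziness does not.
- Section 8 requires intolerance that stops treatment to be recorded as an adverse experience.
- The dosing-day forms record vomiting and its time.

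**Size.** The protocol gives no AE or symptom rate, so no under-count can be computed. For scale only, one patient whose sole event was such a sign would move the proportion of patients with an AE by 1/145 = 0.7 percentage points. That says nothing about how many such patients there would be.

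**The case against.** The strongest defence is that section 12.1 is a coherent rule. It keeps the symptoms of the presenting disease out of the AE tables, and it gives staff three grounds for an exception. A sign that appears or worsens after dosing can fairly be called an evolution. Section 12.3 trains staff to notice these same signs, the checklist collects symptoms in any case, and the predefined list, which is not shown, may name nausea or dizziness outright. In a single-arm study, recording every early malaria symptom as an AE would raise the crude rate and leave attribution to the same judgement.

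Most of this stands, and it limits the point. It does not remove it: the grounds for exception permit recording without requiring it, and no text gives the list, the checklist or section 12.3 priority over the exemption.

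A reader might infer more than the documents support:

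- **That worsening signs cannot be recorded.** Evolution is named as a ground for recording them.
- **That AE rates will be materially understated.** No rate is given, and attentive staff may record these signs.
- **That liver toxicity would be missed.** Liver tests do not depend on reported symptoms.
- **That sections 12.1 and 12.5 formally contradict each other.** Section 12.5 governs only what is already an AE; the two sit awkwardly together but can both be followed.
- **That the whole exemption should give way to a D0 comparison.** That would turn routine early fever or chills into AEs with little gain.

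**Conclusion.** The point holds as a low-severity improvement to a definition. As written, section 12.1 allows a mild section 12.3 sign that is new or worse soon after dosing to be attributed to malaria before recording, and so to bypass the drug-relationship assessment. The effect is confined to AE reporting, an other secondary endpoint. The primary efficacy endpoint and the main secondary endpoint, hepatic laboratory values, are untouched.

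Two assumptions carry the conclusion. Staff must regard signs such as fatigue, nausea, abdominal pain or dizziness as malaria-typical, which is a clinical reading because the protocol names no typical signs. And the predefined list and patient chart, which are not shown, must not already contain a rule that settles the matter.

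**What to change.** Add to section 12.1 that any sign named in section 12.3 that is new, or worse than on the D0 symptoms checklist, is recorded as an AE with its presumed cause (malaria, study drug or other). Keep the present exemption, with its staff override, for other malaria-typical signs such as fever and chills.

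This takes one or two sentences and no new visits or samples, because the checklist is already scheduled at D0 and every later visit. Three small items may follow:

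- a simple intensity grade on the checklist, if it has none, so that worsening can be shown;
- a presumed-cause item on the AE record, if the chart lacks one;
- keeping the checklist with the case record, because the D0 form in Appendix 3 has no symptom field beyond fever history.

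The downside is more AE entries and a somewhat higher crude AE rate. Showing the AE table separately by presumed cause deals with that.
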